### 8.3 Exploratory Assessments

All exploratory tests data will be listed.

Change from baseline in the average daily frequency of moderate to severe VMS will be summarized by treatment group of A01 and overall (Table 14.2.1).

Similar analyses will be conducted for VMS severity score. (Table 14.2.2).

The Plot of Mean change from baseline in VMS frequency and severity will be generated. (Figure 14.2.1, Figure 14.2.2). The Plot of observed mean values of VMS frequency and severity will be generated. (Figure 14.2.3, Figure 14.2.4).

The change from baseline in total and each domain score of the MENQOL will be summarized by treatment group of A01 and overall. (Table 14.2.3)

### 8.4 Dose Change

All subjects were treated with MT-8554 10 mg initially. Then from protocol amendment 4, all subjects remaining in study changed to MT-8554 5 mg. Some subjects already completed or discontinued the study. To compare the data before and after the dose change, the following analyses will be conducted.

No.	Title of Table	Analysis Population
14.1.5	Summary of Exposure to Study Medication: Duration of exposure the dose change	SAF
14.3.1.1	Summary of Treatment Emergent Adverse Events (TEAE)	SAF
14.3.1.1.Ex4Site	Summary of Treatment Emergent Adverse Events (TEAE -Exclude 4 Florida site-	SAF

No.	Title of Table	Analysis Population
14.3.1.2	Incidence of Treatment Emergent Adverse Events by System Organ Class, Preferred Term	SAF
14.3.1.2.Ex4Site	Incidence of Treatment Emergent Adverse Events by System Organ Class, Preferred Term -Exclude 4 Florida site-	SAF
14.3.1.4	Incidence of Treatment Emergent Adverse Events by System Organ Class, Preferred Term and Severity for before the dose change	SAF
14.3.6.1	Transvaginal Ultrasound (TVU)	SAF
14.3.6.1. Ex4Site	Transvaginal Ultrasound (TVU) -Exclude 4 Florida site-	SAF
14.3.6.2	Transvaginal Ultrasound (TVU) - Endometrial Thickness	SAF
14.3.6.2. Ex4Site	Transvaginal Ultrasound (TVU) - Endometrial Thickness -Exclude 4 Florida site-	SAF

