## **6. GENERAL CONSIDERATIONS**

### **6.1 Descriptive Statistics**

Continuous data will be summarized descriptively using the number of observations, mean, standard deviation (SD), median, minimum and maximum. Categorical data will be summarized using frequency counts and percentages. The denominator for the percentages will be the total number of subjects in the treatment group and analysis population being presented, unless otherwise specified.

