### **7.3.1.4 Duration of exposure and Cumulative Dosing Count**

The duration of exposure is calculated as the total number of days that the subject has been treated with study A02 medication—that is, from the study A02 treatment start date to the date of their EOT/withdrawal visit. For subjects lost to follow up, the treatment end date is taken to be the date of their last visit. Interruptions, compliance, and dose changes are not taken into account for duration of exposure.

Duration of exposure (days) = date of end of treatment visit – date of first dose of study A02 medication; Cumulative Dosing days= Duration of exposure – number of days subject miss the medication.

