### 7.3.2.3 Duration of the AE and Time to the AE

Duration of the AE and time to the AE occurrence from start of study A02 medication will be calculated and presented in days, where AE duration = AE stop date – AE start date + 1 and the time to the AE occurrence = AE start date – first study A02 dose date + 1.

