### **8.2 Safety Assessments**

#### **8.2.1 Adverse Events**

The frequency and incidence of TEAEs will be summarized by System Organ Class (SOC) and Preferred Term (PT) by treatment of study A01 and overall.

Following summaries will be presented:

- Overall summary of TEAE (Table 14.3.1.1)
- TEAEs by SOC and PT (Table 14.3.1.2)
- TEAEs by SOC, PT and time of onset (Table 14.3.1.3)
- TEAEs by SOC, PT and severity (Table 14.3.1.4)
- TEAEs leading to discontinuation of study medication by SOC and PT (Table 14.3.1.5)
- Serious TEAEs by SOC and PT (Table 14.3.1.6)
- TEAEs by SOC, PT and relationship (Table 14.3.1.7)
- [REDACTED]

- Adverse drug reactions by SOC and PT (Table 14.3.1.9)
- Serious adverse drug reactions by SOC and PT (Table 14.3.1.10)
- TEAEs by SOC and PT for AEs with frequency  $\geq 3\%$  (or 5%) (Table 14.3.1.11)
- [REDACTED]

For each of the summaries will be done at the subject level - multiple occurrences of the same event within a subject will be counted once in the summaries by SOC and PT; multiple occurrences of the same event within a subject will be counted once in the maximum intensity category (severe > moderate > mild) and/or maximum drug relationship category (reasonable possibility, no reasonable possibility) and/or the earliest occurrence. If intensity or relationship is found to be missing the most severe occurrence will be imputed for that particular summary.

All AEs for each subject, including multiple occurrences of the same event, will be presented in full in a comprehensive listing including subject number, severity, seriousness, action taken, outcome, relationship to treatment, onset/stop date and duration.

Deaths that occur during the study will be listed in a data listing. The data listings for serious TEAE and TEAE leading to discontinuation will be generated as well.

[REDACTED]

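### The two visible adverse event tables for the period after the dose change keep women who never took 5 mg in the denominator, and exposure on each dose is not clearly defined

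*SAP*

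**What the plan says.** SAP 8.4 says that everyone began on 10 mg and that women still in the study moved to 5 mg under amendment 4. It adds: "Some subjects already completed or discontinued the study". It then gives its purpose: "To compare the data before and after the dose change, the following analyses will be conducted". Protocol 5.1 makes the move depend on renewed consent.

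Two AE tables have titles that name the period after the change: 14.3.1.1.B.Ex4Site (overall TEAE summary) and 14.3.1.2.B.Ex4Site (by SOC and PT). Both are in the SAP 8.5 list with population SAF. SAP Table 2 counts a woman in SAF once she has taken any study drug, whatever the dose. The only restriction that 8.5 states is the removal of four sites.

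The default in SAP 6.1 is: "The denominator for the percentages will be the total number of subjects in the treatment group and analysis population being presented, unless otherwise specified".

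On exposure, SAP 7.3.1.4 says: "Interruptions, compliance, and dose changes are not taken into account for duration of exposure". Row 14.1.5 in the 8.4 list nevertheless reads "Summary of Exposure to Study Medication: Duration of exposure the dose change", a title that seems to have lost a word. On counting, SAP 8.2.1 says that "multiple occurrences of the same event within a subject will be counted once in the summaries by SOC and PT". The TEAE columns are the A01 treatment groups and overall.

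**The concern.** A comparison of two dose periods needs each percentage to be taken over the women who were at risk in that period. Every woman was at risk on 10 mg. Only those who stayed and reconsented were at risk on 5 mg. If both tables use SAF, the second includes women who could not have had an event on 5 mg, and the 5 mg percentage falls for a reason unrelated to the drug.

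A second difficulty remains after the denominator is corrected. Each woman is counted once, and time on each dose may differ. Without exposure for each dose, a reader cannot tell a lower event rate from a shorter time at risk. Long-term safety is the primary objective, and this is the planned look at safety across the two doses, so an artificially low 5 mg figure could be taken as better tolerability.

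**Working it through.** The plan has no figure of its own to reproduce. SAP 3.3 gives no sample size calculation, and the analyses are descriptive.

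**Inputs from the documents.** The tables are labelled SAF (SAP 8.5). SAF covers any study drug at any dose (SAP Table 2). The denominator is the whole population presented (SAP 6.1). All started on 10 mg and not all went on to 5 mg (SAP 8.4).

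**Inputs not in the documents.** The number who took 5 mg (n5), the time on each dose and the event rates are all assumed below.

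**Step 1: period after the change.** Let x be the number of women with a TEAE after their own switch. All of them are among the n5.

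- Percentage among women who took 5 mg: p5 = x / n5
- Percentage printed under 6.1: x / N_SAF = p5 × f, with f = n5 / N_SAF
- Relative lowering: 1 − f

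The lowering is therefore the fraction that did *not* switch. With f = 0.75 the printed figure is 25% too low in relative terms.

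**Step 2: period before the change.** All SAF women took 10 mg, so the matching factor is N_SAF / N_SAF = 1. Only the 5 mg side moves.

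**Step 3: size over an assumed range of f.**

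| f | p5 = 40% prints as | p5 = 20% prints as |
|---|---|---|
| 0.25 | 10% | 5% |
| 0.50 | 20% | 10% |
| 0.75 | 30% | 15% |
| 0.90 | 36% | 18% |

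In whole women out of 364, the 40% column becomes 36/364 = 9.9%, 73/364 = 20.1%, 109/364 = 29.9% and 131/364 = 36.0%. The figure 364 is the planned maximum over all sites. It is not the denominator of the two tables, which leave out four sites. The factor f works in the same way at any N, and it may differ between the A01 columns.

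**Step 4: time on each dose.** Assume the same constant event rate on both doses, a mean of 0.6 years on 10 mg for all women, 0.4 years on 5 mg for those who switched, and f = 0.50.

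| Rate per subject-year | Before: 1 − exp(−0.6 × rate) | After, 5 mg takers: 1 − exp(−0.4 × rate) | After, SAF: × 0.50 |
|---|---|---|---|
| 1.0 | 45.1% | 33.0% | 16.5% |
| 0.5 | 25.9% | 18.1% | 9.1% |

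There is no dose effect in either row. In the first row, the drop from 45.1% to 33.0% comes from shorter time at risk, and the further drop to 16.5% from the denominator. Correcting the denominator alone would leave the first part in place. The direction of that part depends on which dose was taken for longer, which the documents do not say.

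**The case against.** **Scope.** A reader might infer that every table in SAP 8.4 has this fault. The documents do not show that. No row in 8.4 has a title naming the period after the change. The two tables that do are in 8.5, which calls its analyses exploratory and excludes four sites. An all-sites version produced to meet the stated aim of 8.4 would have the same problem, but none is visibly listed.

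**Size.** A reader might also infer a several-fold distortion. That needs a low fraction switched, and the documents give none. At f = 0.90 the denominator effect is a relative 10%.

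**Override.** SAP 6.1 allows another denominator where one is specified, and a programmer might use the 5 mg takers without being told. Parts of 8.2.1 and of the contents list are redacted and could hold such a rule. This stands as a limit on confidence. Nothing visible in 8.4 or 8.5 supplies the override.

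**Exposure.** Row 14.1.5 shows that exposure around the change is probably intended, so it would be wrong to say that it was overlooked. What is missing is a derivation, and the general rule in 7.3.1.4 points the other way.

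**Assignment of events.** A reader might say that the SAP has no way to assign an event to a dose. The before and after titles, a TEAE definition based on start or worsening (SAP 7.3.2.1) and recorded onset dates (Protocol 8.6) largely imply assignment by onset. What stays open is the boundary cases: the switch day, the same event in both periods, and the 30-day follow-up. SAP 7.3.2.3 does not settle these, because it measures "Duration of the AE and time to the AE occurrence from start of study A02 medication will be calculated and presented in days" and not from the switch.

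**Other rows.** The ultrasound rows in 8.4 do not name a period, and their scan schedule is a limit of the design and not an error. The title of 14.3.1.4, which names only the period before the change, looks clerical.

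**Conclusion.** The point holds for the two visible tables. Followed as written, the SAP multiplies each 5 mg percentage by f and leaves the 10 mg percentage unchanged, so 5 mg looks better than it was whenever any SAF woman never took it. SAP 8.4 itself says that some women had already gone, so f is below 1. How far below is unknown, and the 10% to 36% for a true 40% is an assumed range and not an estimate. The exposure text needs reconciling as well, because crude percentages for the two periods cannot be read without time on each dose.

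This should be fixed before database lock, with moderate confidence because of the redactions. A reader might go further and conclude that the primary safety analysis is biased. It is not: the overall TEAE summaries cover all A02 treatment, and SAF is the right denominator there.

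**What to change.** In SAP 8.4, 8.5 and 7.3.1.4:

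- (a) For every AE table on the period after the change, including the .B tables in 8.5, use as denominator the SAF women with at least one 5 mg dose. Apply this within each A01 column and overall.
- (b) Derive exposure separately before and after each woman's first 5 mg dose, complete the title of row 14.1.5, and reconcile 7.3.1.4 with it.
- (c) Confirm that a TEAE belongs to the period in which it started or worsened. Add a rule for the switch day, for repeats across periods and for the 30-day follow-up.
- (d) Optionally, show events per subject-year on each dose beside the crude percentage. Add a note that rates do not remove time trends or selection by staying and reconsenting. For example, suppose there is no dose effect, the 52-week risk is 30%, and half of the 52-week hazard falls in the first 8 weeks. Then 30 weeks on 10 mg followed by 15 weeks on 5 mg still gives 48.9 against 21.1 first events per 100 subject-years.

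The cost is a few sentences and a little more programming. Onset dates are recorded (Protocol 8.6), and the change has its own unscheduled visit (Protocol 7.4). If the date of the first 5 mg dose was not captured, the SAP should say that the visit date stands in for it.

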3 STUDY DESIGN

3.1 Overall study design

Study MT-8554-A02 is an open-label, long-term safety extension trial of Study MT-8554-01. The study will be initiated during the conduct of Study MT-8554-A01.

[figure not shown]
Subjects who complete the preceding trial (Study MT-8554-A01) and comply with eligibility criteria for Study MT-8554-A02 will be enrolled in a 52-week open-label treatment period. Visit 7 (Week 12) of Study MT-8554-A01 will be considered Visit 1 of Study MT-8554-A02. Assessments already carried out at Visit 7 (Week 12) of Study MT-8554-A01 will not be repeated. During the 52-week open-label treatment period, subjects will attend visits every 8 weeks between Visits 1 and 3 (Weeks 12, 20, and 28) and every 12 weeks between Visits 3 and 6 (Weeks 28, 40, 52, and 64).

All enrolled subjects will receive MT-8554 (was 10 mg initially, switched to 5 mg*) for 52 weeks. Study drug will be administered once daily before bedtime.

An End of Study (EOS) Follow-up visit will be conducted by phone for safety follow-up 30 days after the end of the open-label treatment period (see Figure 1).

*Note: Based upon the results of Study MT-8554-A01, the dose is changed from 10 mg to 5 mg because participating subjects will no longer derive potential clinical benefit from receiving 10 mg dose. All participating subjects who reconsent to continue the study will receive MT-8554 5 mg.

Figure 1 Study Design Schematic

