4.5 Withdrawal of individual subjects

4.5.1 Discontinuation from treatment

Investigators may choose to temporarily or permanently discontinue study treatment for any reason, including AEs or tolerability.

If any clinically significant abnormality is detected on the clinical breast exam (see Section 6.5.2) at baseline or anytime during the study or there is any occurrence of unexplained uterine bleeding, study medication should be discontinued and subject should be referred to the specialists for further investigations per current standards. If all the required investigations such as physical examination of the breast, imaging and pathology are negative and available within 6 weeks, subject can resume study medication.

An unscheduled study visit can be used to reassess subject's symptoms and willingness to resume study drug.

If treatment is discontinued and the subject is not willing to resume study medication, every effort should be made to continue the subject on study, e.g., attending study visits and carrying out study procedures through to the final visit. For subjects declining to continue on the study, see Section 4.5.2.

The Suspension interval (start and end dates of suspension) and reason for suspending treatment must be recorded in source documents and the electronic Data Collection Form (eCRF).

Subjects who become pregnant during the study should be withdrawn from study treatment. Also see Section 8.8 for necessary documentation and procedures for following up with the subject.

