## 8.5 Exploratory Analysis Excluding Some Study Sites

During the MT-8554-A01, the Sponsor observed a significant degree of study drug non-compliance at a few study sites, where some of these were clustered geographically and had study subjects duplication.

The Sponsor also observed 8 study sites (site number 104, 108, 112, 114, 119, 128, 144, and 158) with significant IP non-compliance based on MT-8554 PK levels. Among them, 4 sites (site number 104, 112, 114, and 119) had highest number of IP non-compliance based on PK levels, were among the high enrollers (site number 112 and 114 were top enrollers and 104 and 119 were among the top 8 enrollers), and were located at a close proximity to each other in the South Florida. The Sponsor initiated a comprehensive re-review to verify the operational conduct of the study.

The Sponsor's review team concluded that at these 4 Florida sites, training and monitoring was conducted similar to all other sites as per standards, and no concerns were identified by the study monitors during the conduct of the study. The Sponsor considered the possibility that the subjects' poor IP compliance could be due to early onset adverse events which might have prevented them from continuation of MT-8554. However, it was noted that there was a lack of adverse events reporting from these 4 Florida sites in comparison to the all others sites. The incidences of AEs at these 4 sites were 31.8, 37.0, 31.6 and 4.3% as compared to 44.1, 39.7, 49.3 and 64.3% at the other sites in placebo, 1, 5, and 10 mg groups respectively, in MT-8554-A01.

Of these 4 sites, one site was identified a duplicate subject during the screening period, which was dropped out of the study. The Sponsor conducted an additional database search to exclude unidentified duplicate subjects. The Sponsor identified 12 subjects at these 4 Florida sites, which were suspected of being duplicates based on date of birth, height, weight medical history, and medications. Later, all these 12 subjects were confirmed by the quality assurance review of the sites as being duplicates, at least one subject at each site.

Therefore, it was considered to conduct the statistical analyses without the data from these sites. As the exploratory analyses, the main efficacy and safety analyses specified as following list will be performed with the ITT and safety population excluding the 4 sites subjects.

No.	Title of Table	Analysis Population

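### The before/after dose-change AE tables in SAP 8.4 cannot measure a dose difference: dose is confounded with time since first A02 dose, period length and selection

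*SAP*

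**What the plan says.** SAP 8.4 sets out the sequence: "All subjects were treated with MT-8554 10 mg initially". "Then from protocol amendment 4, all subjects remaining in study changed to MT-8554 5 mg". It adds: "Some subjects already completed or discontinued the study". Protocol 3.1 puts a second filter on the 5 mg period: "All participating subjects who reconsent to continue the study will receive MT-8554 5 mg". Protocol 10.1 confirms that nobody is randomized, and no washout is described.

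SAP 8.4 then gives the purpose of its table list: "To compare the data before and after the dose change, the following analyses will be conducted". The list covers exposure (14.1.5), TEAE tables (14.3.1.1, 14.3.1.2, 14.3.1.4) and ultrasound tables, all in the safety population. The list in SAP 8.5 shows the form of the contrast: paired .A and .B TEAE tables for before and after the change, there without four sites.

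The rules that feed these tables are general:
- SAP 8.2.1 counts each woman once per event term.
- SAP 6.1 divides by everyone in the group and population presented.
- SAP 7.3.2.1 defines a TEAE by onset or worsening from first dose, with no version by dose period.
- SAP 7.3.1.4 ignores dose changes when it computes exposure.

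**The concern.** The comparison has a fixed order and no concurrent control. The 10 mg period contains each woman's earliest A02 time and everyone who left before the switch. The 5 mg period contains only later time, in women who stayed and agreed to continue. Loss related to tolerability before the switch is foreseeable, because Protocol 4.5.1 states: "Investigators may choose to temporarily or permanently discontinue study treatment for any reason, including AEs or tolerability". An event that starts on 10 mg and persists unchanged on 5 mg counts only in the first period. The two periods also differ in length from woman to woman.

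Long-term safety is the primary objective, and SAP 8.5 reports A01 AE incidence at the other sites of 49.3% on 5 mg and 64.3% on 10 mg. A before/after difference in the same direction could be taken as long-term confirmation when time on drug or selection alone could produce it.

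**Working it through.** The plan states no sample size calculation, alpha, effect size or AE time course, so there is no figure of its own to reproduce. The check asks what the planned contrast would show if dose had no effect.

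**Hand calculation.** Assumed inputs: a first-AE hazard of 0.04, 0.02 or 0.01 per week in A02 weeks 0 to 8 and 0.01 afterwards; 52 weeks in all; no dropout; one switch week. For each period, H = sum of (hazard × weeks), incidence = 1 − exp(−H), and rate = H ÷ weeks. Example, early hazard 0.04 and switch at week 26:
- before: H = 8 × 0.04 + 18 × 0.01 = 0.50, incidence 39.3%, rate 0.50 ÷ 26 × 52 = 1.00 per person-year;
- after: H = 26 × 0.01 = 0.26, incidence 22.9%, rate 0.52 per person-year; ratio 0.52.

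| Early hazard | Switch week | H before | H after | % before | % after | Rate ratio after/before |
|---|---|---|---|---|---|---|
| 0.04 | 13 | 0.37 | 0.39 | 30.9 | 32.3 | 0.35 |
| 0.04 | 26 | 0.50 | 0.26 | 39.3 | 22.9 | 0.52 |
| 0.04 | 39 | 0.63 | 0.13 | 46.7 | 12.2 | 0.62 |
| 0.02 | 13 | 0.21 | 0.39 | 18.9 | 32.3 | 0.62 |
| 0.02 | 26 | 0.34 | 0.26 | 28.8 | 22.9 | 0.76 |
| 0.02 | 39 | 0.47 | 0.13 | 37.5 | 12.2 | 0.83 |
| 0.01 | 13 | 0.13 | 0.39 | 12.2 | 32.3 | 1.00 |
| 0.01 | 39 | 0.39 | 0.13 | 32.3 | 12.2 | 1.00 |

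With an early excess, the rate ratio always favours 5 mg. The crude percentage follows period length as well: in the last two rows nothing differs between the periods except their length.

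**Simulation, no dose effect** (200,000 women per scenario, weekly steps). Assumed inputs: 55% AE risk by week 12, chosen between the 49.3% and 64.3% in SAP 8.5; an early excess that decays with a 6-week constant; gamma frailty; a chance of stopping after each AE; background dropout of 0.4% per week; and staggered entry. In the first five rows the switch is spread over A02 weeks 2 to 56.

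| Mechanism | % before | % after | Rate ratio |
|---|---|---|---|
| Neither | 74.2 | 70.2 | 1.00 |
| Early excess 3:1 only | 69.5 | 53.2 | 0.75 |
| Frailty (variance 1) and 15% stopping per AE only | 58.6 | 52.6 | 0.87 |
| Both | 54.7 | 40.1 | 0.65 |
| Both, early excess already spent in A01 | 46.4 | 40.2 | 0.87 |
| Both, most women switching early (weeks 2 to 60) | 45.1 | 50.7 | 0.58 |

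Across all scenarios with at least one mechanism, the rate ratio was 0.37 to 0.87. In the row with both mechanisms, 68.25% of women reached 5 mg. Dividing by the whole safety population instead would turn 40.1% into 0.6825 × 40.1 = 27.4%, so the missing denominator rule matters too.

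**Effect of aligning time.** A Mantel-Haenszel rate ratio stratified by week since first A02 dose was 0.99 to 1.02 in every scenario. Unstratified person-time rates did not remove the bias; they are the 0.37 to 0.87 above.

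**The case against.** The strongest case against is that these are descriptive tables in an uncontrolled extension. They carry no test, and the documents tie no decision to them. The stated reason for changing dose is loss of potential benefit at 10 mg, not tolerability. TEAEs are shown by A01 arm, Table 14.3.1.3 gives time of onset, the AE listing gives onset and stop dates, and Table 14.1.5 addresses exposure around the change. Two AE table entries in SAP 8.2.1 are redacted. All of this stands, and it makes the risk one of misreading, not type I error. It does not remove the confounding: Table 14.3.1.3 is not in the 8.4 list and is not stated to be split by dose, and 8.4 gives its purpose as a comparison.

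Four stronger readings are tempting, and the documents do not support them:
- A reader might infer that 5 mg will look safer whatever the truth. The crude percentages, which are what the visible SAP plans, can reverse, as the week-13 rows show.
- A reader might take SAP 8.5 as evidence of an early AE hazard, because it says poor compliance "could be due to early onset adverse events which might have prevented them from continuation of MT-8554". That is a hypothesis about A01 non-compliance at four sites, and the next sentence counts against it by noting how few AEs those sites reported. No AE time course is given for A02.
- A reader might suppose that the 10 mg period holds every woman who left because of an AE. It holds only those who left before the switch.
- A reader might treat all women as newly exposed. Entrants completed A01 through Week 12, and only those from the placebo arm were drug-naive.

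It is also fair that the switch followed A01 results, so the earliest A02 weeks may hold little or no 5 mg time. This limits the remedy; it does not rescue the crude contrast.

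**Conclusion.** The point holds in limited form and should be addressed before the SAP is final. Within each woman, dose is fully confounded with time since first A02 dose, and between periods it is confounded with length of follow-up and survivor selection. Nothing visible in the plan corrects for this. If AEs cluster early or AE-prone women leave before the switch, rates lean toward 5 mg with no dose effect: about 0.35 to 0.87, and 0.87 where the early excess was already spent in A01. That range rests on assumed hazards, frailty, stopping and switch times. It also describes person-time rates, which the visible SAP does not plan. The true size cannot be found from the documents. The planned percentages do not measure a dose difference in either direction.

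The point does not extend to ultrasound, which is scheduled only at Week 12 and at Week 64 or early termination. A reading on 5 mg there reflects 10 mg followed by 5 mg, with no clear direction of bias.

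**What to change.** In SAP 8.4:
1. Define TEAEs, denominators and person-time by dose period. The denominator for the after tables should be women who received 5 mg. Reconcile this with SAP 7.3.1.4, which ignores dose changes, and with Table 14.1.5.
2. Add TEAE rates by dose within common intervals since first A02 dose, for example weeks 0–8, 8–16, 16–28, 28–40 and 40–52. Compare doses only in intervals with person-time on both, separately for A01 placebo and A01 active women. This is possible because some women had already completed when the change came, so time since first dose at the switch varied.
3. List events ongoing at the switch separately, so that they do not appear as absent on 5 mg.
4. Label the crude before/after tables as descriptive and not a dose comparison, and state that selection by reconsent and by entry cohort remains even after time alignment.

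The cost is SAP wording and one or two extra tables from dates already collected. Cells will be sparse, and early intervals may have no 5 mg data and so give no comparison.
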